This document is confidential and is to be distributed for review only to investigators, potential investigators, consultants, study staff, and applicable independent ethics committees or institutional review boards. The contents of this document shall not be disclosed to others without written authorization from the Principal Investigator.

Protocol Summary

Full Title:	Randomized controlled trial assessing transperineal prostate biopsy to reduce infection complications
Clinical Phase:	II
Principal Investigator:	[name]., M.P.H.
Sample Size:	N= 1,702
Study Population:	Men who are aged at least 18 years with: history of Grade Group 1 or 2 prostate cancer, first diagnosed prior to date of planned biopsy (active surveillance cohort); clinical concern for the presence of prostate cancer as determined by the treating urologist and prior negative prostate biopsy performed ≤36 months prior to date of planned biopsy (prior negative cohort); Men without previous prostate biopsy (first time prostate biopsy)
Accrual Period:	Approximately 31 months
Study Design:	Prospective, randomized trial with 1:1 ratio to either the transperineal or transrectal biopsy group. Participants will be assessed for adverse events, pain and discomfort immediately and 7 days post-biopsy.
Intervention Description:	Transrectal prostate biopsy (TR-Bx) under local anesthesia is currently the most commonly used approach to evaluate for the presence of prostate cancer. A limitation of TR-Bx is the need for biopsy needles to pass through the rectal mucosa on their trajectory to the prostate, placing men at high risk of an infectious complication. An alternative method for performing prostate biopsy is via a percutaneous transperineal approach. One limitation of transperineal prostate biopsy (TP-Bx) has been the historic need for it to be performed under general or spinal anesthesia in order for patients to tolerate the multiple required needle passes through the perineal skin. Due to recent technical advances TP-Bx may now be safely performed under local anesthesia.
Primary Objective:	To compare infection adverse events of TP-Bx vs. TR-Bx performed under local anesthesia.
Secondary Objectives:	To compare other adverse events such as bleeding and urinary retention. To compare detection rates of clinically significant and insignificant prostate cancer.

SCHEMA

[figure not shown]

Table of Contents

1. STUDY OBJECTIVES	7
2. BACKGROUND.....	7
3. SUBJECT SELECTION	8
3.1 Study Population	8
3.2 Inclusion Criteria.....	8
3.3 Exclusion Criteria.....	8
4. STUDY PROCEDURES.....	9
4.1 Study Enrollment and Randomization.....	9
4.2 Data Collection & Confidentiality.....	10
4.3 Study Calendar	11
4.4 Antibiotic Administration	12
4.5 Biopsy Procedure	12
4.6 Duration of Follow Up	12
5. MEASUREMENT OF OUTCOMES	13
5.1 Adverse events.....	13
5.2 Pain, Anxiety and Discomfort	14

5.3 Biopsy Pathology	14
6. STATISTICAL CONSIDERATIONS	15

1. Study Objectives

Primary Objective: The primary objective of this study is to compare the incidence and severity of infectious complications between the transperineal and transrectal approaches to prostate biopsy.

Secondary Objectives: Secondary objectives of this study include comparing the incidence of other adverse events, associated pain, and cancer detection rates between the transperineal and transrectal approaches.

2. Background

Approximately one million transrectal prostate biopsies (TR-Bx) are performed annually in the United States.¹ The number of prostate Bx is expected to increase due to the demographic growth of the aging male population. Moreover, 44% of U.S. men undergoing initial biopsy report having a repeat biopsy within five years.² Additionally, more than half of men diagnosed with prostate cancer currently opt for active surveillance, which requires serial repeat biopsy to monitor for disease progression.³ Therefore, biopsy use will only increase with greater adoption of active surveillance and the greater number of aging men. The safety and effectiveness of this common procedure will impact 1 out of 3 U.S. men at least once during their lifetimes when they undergo biopsy.

Due to the need for biopsy needles to pass through the rectal mucosa on their trajectory to the prostate, TR-Bx is associated with a significant risk of infectious complications. The needle travels through the “dirty” rectal mucosa to the “clean” prostate at least 12 times,⁴ and fecal flora may seed the vascular prostate gland and bloodstream, leading to infection.^{5,6} One systematic review suggests this rate may be as high as 5%.⁷ The United States Preventive Services Task Force (USPSTF) Grade C recommendation for PSA screening considered adverse events associated with biopsy among the harms of PSA-based screening.⁸ Despite antibiotic prophylaxis, 44% of men experience bacteriuria and 16% experience bacteremia after TR-Bx.⁹

Furthermore, the risk of post-biopsy infection has increased in recent years due to the growing incidence of antibiotic resistance.¹⁰ Nam first reported an alarming four-fold, population-based increase in post-Bx infection hospital admissions from 0.6% in 1996 to 3.6% in 2005 among 75,190 patients.¹¹ In particular, men with fluoroquinolone-resistant bacteria in the rectum are at increased risk for post-Bx infection and sepsis,¹² which can result in dire complications such as limb gangrene/amputation, endocarditis, meningitis, disseminated intravascular coagulation (DIC) or death.^{13–18}

As an alternative to the transrectal approach, prostate biopsy may be performed percutaneously through the perineal skin. Due to avoidance of the rectum, transperineal prostate biopsy (TP-Bx) is associated with an overall lower risk of infectious complications. At some centers, this has obviated the need for perioperative antibiotics, which is reinforced by the Society of Interventional Radiology Guidelines.^{19,20} One additional benefit of TP-Bx is that this procedure offers better sampling of the anterior prostate, which is missed with the transrectal approach in men with larger prostate volumes due to benign prostatic hyperplasia.²¹ The biopsy core excursion is 2 cm, and therefore sampling of the anterior prostate from the rectum is limited. In contrast, the TP approach has relative ease of access to the anterior prostate.⁶ This is reflected

in greater detection of clinically significant prostate cancer in retrospective studies with transperineal²²⁻²⁵ under general anesthesia (49%-91%) vs. transrectal^{24,26-31} Bx approaches (14-42%). Given more than 80% of first-time biopsy nationally are performed without MRItargeting,^{32,33} the utility of in-office transperineal vs. transrectal MRI-targeted biopsy must be evaluated as this applies to a large population of men. For instance, the American Urological Association professional guidelines were updated to recommend MRI use for first-time biopsy in early 2020;³⁴ however, lack of insurance coverage and limited access for urologists to the costly MRI-targeted biopsy platform contribute to a large population of men who need to be evaluated in the repeat biopsy setting of active surveillance and prior negative biopsy.

Despite the aforementioned benefits of TP-Bx, this procedure has seen limited adoption due to the historic need for it to be performed under general anesthesia in order for patients to tolerate the required multiple needle sticks to the perineal skin. Additionally, because of the need for biopsy needles to traverse the pelvic floor muscles and vascular prostate apex, TP-Bx is believed to have a higher risk for urinary retention and bleeding as compared to the traditional transrectal approach.

In recent years, the development of novel local anesthetic techniques and needle guides has permitted TP-Bx to be performed in the office setting with a more favorable side-effect profile.^{20,35,36} There has, however, been slow adoption of this procedure by only a handful of centers. In fact, national estimates of TP-Bx use place this figure closer to approximately 1-2%.

In this study, we aim to compare the safety, tolerability, and cancer detection rates of TP-Bx versus TR-Bx within the contexts of a randomized clinical trial. The results of this study will provide high level medical evidence regarding which method of prostate biopsy carries the best risk to benefit ratio for men undergoing evaluation for prostate cancer.

3. Subject Selection

3.1 Study Population

This study will include all men who are recommended to undergo prostate biopsy as part of routine clinical care. Inclusion and exclusion criteria are listed in the following sections.

3.2 Inclusion Criteria

- Male sex
- Age ≥ 18 years
- Active surveillance cohort: History of Grade Group 1 or 2 prostate cancer, first diagnosed prior to date of planned biopsy
- Prior negative cohort: Clinical concern for the presence of prostate cancer as determined by the treating urologist and prior negative prostate biopsy ≤ 36 months prior to date of planned biopsy
- Men without previous prostate biopsy (first time prostate biopsy)
- Willingness to sign informed consent and adhere to the study protocol

3.3 Exclusion Criteria

- Acute prostatitis within the last 6 months
- PSA > 20 ng/mL in men who have previously undergone prostate biopsy
- Current non-urologic bacterial infection requiring active treatment with antibiotics
- Unfit to undergo prostate biopsy under local anesthesia

- Prior definitive therapy for prostate cancer, such as radiation therapy or partial gland ablation
- Men who have previously undergone prostate biopsy in whom artifact would reduce quality of prostate MRI (extensive orthopedic pelvic metal)
- Contraindication to prostate MRI (claustrophobia, pacemaker, chronic kidney disease) in men who have previously undergone prostate biopsy

4. Study Procedures

4.1 Study Enrollment and Randomization

Eligible patients will be informed of the study by the study urologist and research staff. Interested participants may also learn more about the study through online resources such as ClinicalTrials.gov or through study informational brochures. All potential subjects will be allowed as much time as needed to consider study participation. Patients choosing to participate in the study will be consented within the privacy of a clinical exam room. Study staff will explain to each potential subject the research objectives, risks and benefits of study participation, and the subjects' rights and responsibilities. For patients who are scheduled for biopsy, electronic consent will also be available via phone. Eligible patients will be contacted by a member of the study team (i.e. investigator or research coordinator), who will explain the study to the patient. The patient will also receive a link to the electronic consent form via email or MyChart message.

This study will utilize either a traditional one-stage or a two-stage consent process. The reason for having the one-stage consent is there are a few sites in which the predominant approach is transperineal. Therefore, this two-stage consent does not work. With the one-stage consent, patients give permission to participate in the study prior to randomization (traditional RCT consent). With a second-stage consent, subjects who meet all eligibility criteria will sign the firststage consent form. Patients will have the option to sign the consent in person or electronically. First-stage consent will register the subject to the study and will allow investigators to use their data from their medical record and post-biopsy questionnaire responses for research purposes. Subjects who sign first-stage consent will be randomized in a 1:1 ratio to receive TP-Bx or TRBx. The patients' first-stage consent or their traditional one-stage consent will be valid for eight months to accommodate for biopsy scheduling. This will reduce the number of re-consents and align with the standard of care timeline for biopsy procedures. Biopsies are often scheduled as far out eight months from their clinic visit.

Participants will be consented remotely using an electronic version of the informed consent form that follows federal, state, and local regulations, as applicable. We will implement the following procedures for electronic informed consent.

The informed consent document(s) will be sent to the subject or their Legal Authorized Representative (LAR), if applicable, via secure email sent by REDCap prior to the scheduled consent discussion. The subject or LAR will be asked to review the consent document prior and during the consent discussion with a study staff member via phone or approved teleconferencing service (i.e., Zoom). The study staff member will confirm the subject or LAR has read and has the capacity to appreciate all aspects of the information presented in the consent process for the research study. The subject or LAR will be encouraged to ask questions. If agreeing to participate, the subject or LAR will sign the consent form using electronic informed consent (eConsent) via REDCap. A computer, tablet or touch screen phone will be used to capture digital signatures. The person conducting consent will also sign the electronic informed consent (eConsent) document in a contemporaneous manner. Subjects will

be provided with a digital copy of the completed form via email. The informed consent discussion and process will be documented by the study team in the subject's medical record or study record.

If a subject does not have access to a touch screen phone, computer or tablet, cannot work with remote electronic informed consent, or the remote electronic informed consent cannot be obtained for any other reasons, the consent may be conducted and documented at an in-person visit prior to study activities via paper consent form or through REDCap on an ITS tagged device.

The assignment sequence will use randomly permuted blocks of unequal size stratified by urologist, PSA (<4, 4-9.9, \geq 10 ng / mL) and biopsy indication (prior negative vs. active surveillance) and implemented by the randomization model in REDCap, which prevents an investigator from learning allocation before a patient is unambiguously registered on study and from changing allocation afterwards, thus ensuring full allocation concealment. For men with prior biopsy, we exclude men with a PSA >20 ng/mL.

For the REDCap randomization model, randomization of subjects will occur on the data collection form where the randomization field is located. Before a subject is randomized, a 'Randomize' button will appear next to that field. When a user (who has been given appropriate 'Randomize' user privileges) clicks that button, a pop-up box will appear that will allow the user to randomize the subject. After a subject has been randomized, the grouping (i.e. transrectal or transperineal biopsy) will become permanently locked and unmodifiable. The randomization field will always be locked and unmodifiable both before and after randomization has occurred for a subject.

Randomization is unblinded, and research coordinators of respective enrolling sites will inform their patients of the assigned cohort.

Subjects randomized to TR-Bx will receive transrectal biopsy. Subjects randomized to TP-Bx will undergo a second consent discussion with the enrolling investigator, where the risks and benefits of transperineal biopsy will be explained. Subjects can then decide whether to undergo standard transrectal biopsy or transperineal biopsy. Subjects who agree to undergo TP-Bx will sign the second-stage consent form.

4.2 Data Collection & Confidentiality

Study data will be prospectively collected from patient medical records and patient surveys. In all participating centers, the site-specific research coordinator will perform baseline data acquisition and medical record abstraction. This data will be entered into standardized clinical report forms housed within a REDCap environment and hosted by WCM. Each patient will be assigned a unique study identifier.

REDCap (Research Electronic Data Capture) is a secure, web-based application designed exclusively to support data capture for research studies. The REDCap platform will be partitioned to permit read/write access only to site-specific records such that individual sites will be able to access records for their own subjects, exclusively. REDCap has a secure email and web-based data collection interface that may be utilized for collecting data. The site-specific research coordinator will determine individual patients' preferred method of survey response

and may collect survey data either through mail, telephone, REDCap, or during an in-person visit.

Only the WCM research coordinator will be able to review de-identified data across sites to conduct data quality checks and share data quality with the study biostatistician.

To ensure accuracy of data entered in the REDCap database from source documents (including surveys and medical record abstract), sites will perform 100% visual review and conduct double data entry for a sample (i.e., 10%) of the data.

Data quality checks will be conducted every 6 months, coinciding with Data Safety and Monitoring reviews.

For protocol deviations fitting immediately reportable criteria, the DSMC's primary concern lies with whether the deviation has the potential to negatively impact subject safety or integrity of study data or whether the deviation places subjects at greater risk of harm (including physical, psychological, economic or social harm). If the DSMC makes determinations that the reported protocol deviation impacts either, it may recommend modifications, suspension or termination of the study.

Interim study findings will be communicated in cases where modifications are recommended. The DSMC will require the PI to submit confirmation to the DSMC that the modification(s) have been made, or to submit a reason why the PI did not agree with the DSMC's recommendation.

4.3 Study Calendar

	Month -8 to Day 0	Day 0	Day 5 to 9
Eligibility	X ^a		
Informed consent	X		
Demographics	X		
Medical history ^b	X		
Physical exam ^c	X		
Randomization	X		
PSA	X		
Rectal swab ^d	X		
Prostate Biopsy		X	
Assessment of Adverse Events ^e			X
Concomitant Medications ^f		X	X

^aTo be performed prior to informed consent. ^bMedical comorbidities, indication for biopsy, multiparametric MRI findings, and history of prior biopsy or infection. ^cHeight and weight. ^dfor transrectal biopsy only.
^eAssessed by patient questionnaire. Events will be grading using Common Terminology Criteria for Adverse Events (CTCAE) v5.0. ^fAssessed by patient questionnaires.

4.4 Antibiotic Administration

For patients undergoing a TR-Bx, antibiotic prophylaxis will be administered in accordance with guidelines from the American Urological Association (AUA).³⁷ No antibiotic prophylaxis will be administered for patients undergoing a TP-Bx.

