5.1 Adverse events

The primary objective of this study is to compare the incidence and severity of infectious complications experienced by patients undergoing TP-Bx versus TR-Bx. Patients will be assessed for complications by way of electronic questionnaire administered 7 ± 2 days post biopsy using a REDCap site hosted at Weill Cornell Medical Center. For patients unable to complete the questionnaire electronically, responses will be obtained via telephone interview. Any patient indicating that they experienced an adverse event will be contacted by the study team to seek further details. Additionally, all relevant medical records will be requested. Adverse events will be classified in accordance with Common Terminology Criteria for Adverse Events (CTCAE) v5.0.

The primary outcomes are infection rates of TP-Bx versus TR-Bx.

The secondary outcomes are patient-reported pain and anxiety, and comparison of noninfectious complications such as bleeding and urinary retention rates, and cancer detection.

Timing for assessment of study variables.			
Assessment	Baseline Pre-Bx	Day of Bx	7-days Post-Bx
Baseline history and physical exam, screening, consent	✓		
Prior Bx (Y/N)	✓		
Prior Bx infection (Y/N)	✓		
PSA	✓		
Indication for Bx	✓		
MpMRI findings	✓		
Randomization: TR-Bx vs. TP-Bx	✓		
Bx infection risk determination for TR-Bx prophylaxis	✓		
Bx completed (Y/N)		✓	
Bx duration (minutes)		✓	
Pain (VAS)		✓	✓
Discomfort (VAS)		✓	✓
TMI Anxiety (Likert 5 levels)		✓	
Decision regret			✓
Adverse events (Y/N) and Bother			
UTI			✓
Sepsis			✓
Urinary retention			✓

Fever	✓
Hematuria	✓
Hematochezia	✓
Hematospermia	✓
UTI diagnosed by HCP	✓
Unplanned HCP contact	✓
Qualitative responses	✓
Bx pathologic outcomes, if cancer:	✓
Gleason grade group(s)	✓
Number of cores positive	✓
Number of cores negative	✓
Maximum cancer core length	✓
Targeted Bx positive (Y/N/NA)	✓
Systematic Bx positive (Y/N)	✓
Location of positive cores	✓

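### Prophylactic antibiotics go only with transrectal biopsy, yet no seven-day item or listed outcome asks about likely antibiotic harms, so the safety comparison is incomplete in a direction that, if anything, disfavors the transperineal arm

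*Combined protocol and SAP*

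**What the plan says.** Section 4.4 sets the antibiotic policy by route. Transrectal biopsy is covered by prophylaxis following American Urological Association guidance. For the other route, "No antibiotic prophylaxis will be administered for patients undergoing a TP-Bx". Two related items also go with transrectal biopsy alone: a rectal swab (Section 4.3, Study Calendar) and the entry "Bx infection risk determination for TR-Bx prophylaxis" in the Section 5.1 table.

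The policy is disclosed and has a stated rationale. Section 2 says: "Due to avoidance of the rectum, transperineal prostate biopsy (TP-Bx) is associated with an overall lower risk of infectious complications". It continues: "At some centers, this has obviated the need for perioperative antibiotics".

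The objectives name the contrast by approach. Section 1 sets out to "compare the incidence and severity of infectious complications between the transperineal and transrectal approaches to prostate biopsy", with other adverse events among the secondary objectives. Section 2 says the results will inform "which method of prostate biopsy carries the best risk to benefit ratio for men undergoing evaluation for prostate cancer".

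The Study Calendar footnote makes the patient questionnaire the source for adverse events, with CTCAE v5.0 grading. Section 5.1 adds a call from the study team and a request for records once a man reports an event.

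**The concern.** Men who undergo transrectal biopsy are exposed to a drug treatment that men who undergo transperineal biopsy are not. Any gastrointestinal or allergic reaction to it is a cost of the transrectal strategy. The plan promises a comparison of other adverse events and speaks of a risk-to-benefit answer, but its main instrument does not ask about these reactions. Avoiding antibiotics is part of the plan's own case for the transperineal route, yet the trial would not systematically measure the harm avoided.

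There is also a smaller point of description. Because prophylaxis can act on infection, a difference between arms, or the lack of one, belongs to route and prophylaxis together. Sections 1 and 6 do not say so.

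**Working it through.** **1. The plan's own figures.** Section 6 gives 682 + 620 + 400 = 1,702 men, randomized equally, so 1,702 / 2 = 851 per arm. It assumes infection rates of 0.5% (transperineal) and 2.0% (transrectal), with one-sided α = 0.10 and power above 80%.

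- Expected infections: 851 × 0.020 = 17.0 and 851 × 0.005 = 4.3, a difference of 12.8 before rounding the two counts.
- Normal-approximation power: standard error under the null = √(2 × 0.0125 × 0.9875 / 851) = 0.00539. Under the alternative it is √((0.02 × 0.98 + 0.005 × 0.995) / 851) = 0.00537. Power = Φ[(0.015 − 1.2816 × 0.00539) / 0.00537] = 0.934.
- One-sided Fisher exact power: 0.920.

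Both agree with the stated figure. None of these inputs changes if safety items are added or the contrast is described more fully.

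**2. What differs between arms.** Route, prophylaxis, and the swab and infection-risk assessment. No purpose is given beside the swab. If it guides prophylaxis, which is an inference, it belongs to the same co-intervention and is not a separate difference.

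**3. What is asked.** The printed seven-day items cover fever, chills, bleeding at three sites, urinary retention, diagnosed urinary infection, new medicines and healthcare contacts. The Section 5.1 table adds sepsis and qualitative responses. Neither lists diarrhea, rash or drug reaction.

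**4. What the indirect routes can pick up.**

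| Route | Limit |
|---|---|
| New-medicine list (Appendix, item 8) | Records use after the biopsy, not reactions; doses taken beforehand fall outside it |
| Unplanned contact (item 9) | Needs the man to seek care and to regard the reason as biopsy-related |
| Community contact (item 10) | Records that a contact occurred, not the symptom |
| Qualitative responses (Section 5.1 table) | No matching item in the printed Appendix |
| Call from the study team (Section 5.1) | Starts only once an event has been reported |
| Medical record abstraction (Section 4.2) | Finds only what a clinician wrote down |

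Section 6 analyzes other biopsy-related complications of grade 2 or above, and a drug reaction could be counted there if it came to light. Its Grade 1 category is described as three patient-reported bleeding symptoms, so a mild reaction has no evident place.

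**5. Direction.** Prophylaxis goes with the transrectal route. Under-recording its harms makes that arm look, if anything, safer than it is. It cannot create a false transperineal advantage, and it does not enter the primary infection endpoint.

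**6. Size.** The documents give no antibiotic adverse-event rate. Over an assumed range, per 851 men:

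- 1%: 851 × 0.01 = 8.5
- 3%: 851 × 0.03 = 25.5
- 5%: 851 × 0.05 = 42.6

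These are events with no dedicated item, not events certain to be lost. The 851 is the number randomized. Under two-stage consent, men allocated to transperineal biopsy may choose transrectal biopsy (Section 4.1), so the number receiving prophylaxis could differ.

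**The case against.** The strongest reply is that nothing here is mis-stated. The antibiotic policy is open and reasoned, the objective says only that approaches will be compared, and Section 6 refers to groups. Randomizing each technique with its own prophylaxis policy is a sound pragmatic contrast. This stands. A reader might infer that the objective credits any difference to route, or that a null result would be reported as showing route does not matter. The documents do not say either. The attribution to avoiding the rectum is in the Background, and no null interpretation is specified. Hence the strategy wording is optional.

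A second reply is that reactions are not wholly uncaptured. That also stands: the routes in the table above exist. The printed form may also be incomplete, since decision regret, bother and seven-day pain appear in the Section 5.1 table but not among the printed seven-day items. What remains is that the table does not list these harms either, so capture is unsystematic on any reading.

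A third concerns size. A reader might note that 1.5% of 851 is 12.8, the whole expected infection difference, and conclude that unrecorded harm could cancel the benefit. That is no finding: 1.5% is simply 2.0% − 0.5%. It also equates a rash or loose stool with an infection needing medical attention, and ignores the background rate of such symptoms in the other arm.

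Finally, no composite weighing of harms is planned, so no pre-specified risk-benefit estimate is biased. This is correct. The consequence is an incomplete comparison of other adverse events.

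**Conclusion.** The point holds as a measurement gap. The trial validly compares transperineal biopsy without prophylaxis against transrectal biopsy with guideline prophylaxis, and does not isolate route. Likely harms of the prophylaxis have no systematic capture, so the secondary adverse-event comparison and the risk-to-benefit aim are incomplete, if anything to the disadvantage of the transperineal arm. The sample size, power and primary test are unaffected.

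The magnitude is unknown. The 9 to 43 events per 851 men rest entirely on an assumed 1% to 5% rate and are not equivalent in severity to infections. The conclusion also assumes that the instrument in use has no drug-reaction item beyond those printed in the Appendix or listed in Section 5.1. This is a cheap improvement to what the trial measures and not a flaw in its validity.

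**What to change.** Add yes/no items to the seven-day questionnaire in both arms: new diarrhea, and new rash or allergic reaction, each since the day before the biopsy. The wording should not mention medicines. An item tied to a drug taken for the biopsy would be near zero by construction in men who undergo transperineal biopsy, and would replace one asymmetry with another. Record separately any clinician attribution to prophylaxis. Grade the events by CTCAE v5.0, add them to the Section 5.1 table, and list them in Section 6 as a secondary safety outcome compared by randomized arm.

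Optionally, add one sentence to Sections 1 and 6 stating that the contrast is between two strategies and that no result isolates route.

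The cost is a slightly longer form, some background noise from unrelated symptoms in an unblinded trial, and a few more follow-up calls. Reactions starting after the day 5 to 9 assessment would still be missed. The items help only men who have not yet completed the form, because mild reactions cannot be recovered reliably later. No change to prophylaxis in either arm is proposed.
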